Most gynecologic and many intra-abdominal malignancies are treated with an initial surgical procedure. Over the past 20 years there has been a dramatic increase in obesity rates in the US with more than one third (35.7%) of US adults being obese ($BMI > 30\text{kg}/\text{m}^2$) or morbidly obese ($BMI > 35\text{ kg}/\text{m}^2$). There is a direct link between obesity and wound complications following surgery with an increasing BMI leading to increasing rates of complications. Negative pressure wound therapy (NPWT) is a system that utilizes sub-atmospheric pressure to improve wound healing by increasing the formation of granulation tissue. NPWT has been shown to improve outcomes in both the orthopedic and cardiothoracic surgery populations. To date, there is no prospective study evaluating the application of prophylactic NPWT in laparotomy patients.

Primary Objective:

To evaluate the rate of wound complications with negative pressure wound therapy (NPWT) as compared to standard surgical closure and post-operative wound care in obese patients ($BMI \geq 35\text{ kg}/\text{m}^2$) undergoing laparotomy for a suspected gynecologic malignancy or other abdominal cancer.

Secondary Objective:

To compare the time between surgery and the start of anti-cancer therapy (chemotherapy and/or radiation therapy) between those patients diagnosed with a malignancy who received NPWT and those who received standard surgical closure

Patient Population:

Morbidly obese ($BMI \geq 35\text{ kg}/\text{m}^2$) adult patients presenting for surgical treatment of a known or suspected gynecologic malignancy or other abdominal cancer by laparotomy incision

Study Procedures:

After screening and obtaining written consent, but prior to surgery 1:1 randomize to either:

- Negative pressure wound therapy (NPWT)
- Standard surgical closure

Assess wound complications at 1st post-operative visit (10-14 days after initial procedure)

If no cancer diagnosis, final study assessment at 1st post-operative visit

If cancer diagnosis is made, chart review at 3 months post-surgery to determine time between surgery and start of anti-cancer therapy (chemotherapy and/or radiation therapy)

Enrollment Goal:

200 patients randomized over 24 months

1.0 Introduction and Overview

Up to 90% of type I (estrogen-dependent) endometrial cancer patients are obese¹ and obesity is considered a risk factor for both endometrial and ovarian cancers². Most gynecologic malignancies are treated with an initial surgical procedure. A number of colorectal diseases are also increased with obesity including diverticular disease and colorectal cancer^{15,16, 17}. A central challenge for surgeons is the increase in the rates of wound complications following surgery given the rise in obesity. The rate of wound complications for gynecologic oncology procedures is 34% overall and is highly correlated with BMI⁴. Patients with a BMI of ≥ 40 kg/m² had a 10 fold increase in the risk of wound complications compared to normal weighted patients⁶. Some patients are able to circumvent this problem with a minimally invasive approach to their surgery; however, obesity increases the risk of conversion to an open procedure. Wound complications are not only distressing to patients but can also delay necessary adjuvant therapy such as chemotherapy and radiation.

Negative pressure wound therapy (NPWT) is a system that utilizes sub-atmospheric pressure to improve wound healing by increasing the formation of granulation tissue. The mechanism for this improved wound healing is thought to be increased local blood flow, mechanical stress at the wound surface, removal of factors that inhibit wound healing and decreased bacterial burden. To date there are good data to show the benefit of using NPWT to treat wound complications that arise post-operatively. In the orthopedic and cardiothoracic surgery literature there is evidence to suggest that prophylactic NPWT placed over a closed incision decreases wound dehiscence and infection rate, with a 40% decrease in orthopedic patients and 4-fold decrease in morbidly obese cardiothoracic patients. However, to date, there is no prospective study evaluating the application of prophylactic NPWT in laparotomy patients.

2.0 Study Objectives

The primary goal of this study is to evaluate if the use of prophylactic negative pressure wound therapy (NPWT) over a closed incision improves postoperative outcomes and cancer care for morbidly obese (BMI ≥ 35 kg/m²) patients undergoing laparotomy for treatment of a suspected gynecologic or other abdominal malignancy is comparable or better to wound healing after standard surgical closure and wound care.

This comparison will be achieved by:

- Assessing the incidence of wound complications, specifically, dehiscence and infection at the 1st post-operative visit (10-14 days after surgery)
- documenting the time from surgery to the start of anti-cancer treatment in a subset of patients receiving a cancer diagnosis by chart review approximately 3 months after surgery

3.0 Background and Significance

The obesity epidemic is a growing problem in the US and its effects are felt very heavily on the gynecologic oncology population. Both endometrial and ovarian cancers are increased in the obese populations^{1,2}, and the majority of gynecologic malignancies are initially treated with a surgical procedure. A number of colorectal diseases are also increased with obesity including diverticular disease and colorectal cancer^{15,16, 17}. Risks and complications of surgery are much greater in the obese population. The reported rate of wound complications in the gynecologic oncology population is 34-40% depending on the location⁴. Wound complications are highly correlated with patient BMI. These wound complications can lead to a delay in necessary adjuvant therapies such as chemotherapy and radiation. It is known that delays in the initiation of adjuvant therapy can have a negative impact on survival.

NPWT is a system that uses sub-atmospheric pressure to alter the physiologic and chemical environment of the wound bed. It is postulated that this works through several different mechanisms including increased local blood flow, increased mechanical stress leading to increases in cellular proliferation, more effective removal of factors that inhibit wound healing including bacteria and fluid^{7,8}. Studies using NPWT in an open laparotomy incision to facilitate healing by secondary intention show that it leads to decreased wound healing time¹⁰. However, to date, there are few studies evaluating the use of prophylactic NPWT over a closed incision, and most of the existing data is in the orthopedic and cardiothoracic surgery literature. The use of prophylactic NPWT over orthopedic wounds has been shown to decrease wound dehiscence and infection rates by 40%, and has decreased the rate of wound complications 4-fold in obese patients undergoing cardiothoracic surgery^{12,13}. However, it is unclear if this same benefit will be seen with abdominal laparotomy incisions.

4.0 Wound Complications at the University Of Minnesota

We performed a retrospective chart review of all patients with a $BMI \geq 30 \text{ kg/m}^2$ who have undergone a laparotomy for a known or suspected gynecologic malignancy at our institution in the past 6 months. We found that of 51 obese patients to undergo a laparotomy, 13 (25%) had some form of wound complication, either a wound dehiscence or infection. This is on par with what is reported in the literature. Further, 5 of the 51 patients were readmitted to the University of Minnesota hospital due to their wound complications, for a readmission rate of almost 10%. The results of this chart review were used to inform our sample size calculations.

5.0 Research Design

This is a randomized controlled trial in which eligible patients will be randomized to either a control or intervention group. All patients undergoing laparotomy for a known or suspected gynecologic or other abdominal cancer will be approached for eligibility. Once all eligibility criteria are met, the patient will be consented both with verbal and

written consent procedures. Following consent the patient will be randomized to either: 1) routine closure of the surgical site (control arm); or 2) closure of the wound with a prophylactic NPWT placed over the closed surgical incision. The standard surgical closure consists of closure of the fascia with a looped PDS suture in a running fashion either with the use of a mass closure technique or a Smead Jones closure at the discretion of the operating surgeon, closure of the subcutaneous space if >2 cm deep, followed by staple or suture closure of the skin. These same steps will be followed for the NPWT group with the addition of placement of the NPWT system over this closed incision. This NPWT system will be removed on post-operative day number 2 or 3, prior to patient discharge from the hospital. The staples, if used, will then be removed in the usual time frame of anywhere from 10 to 21 days post-operatively. This will also allow for standardized evaluation of the patient's wound to determine if there have been any wound complications since their surgery. Patients will be followed for the development of any wound complications including infection, dehiscence and evisceration for 4 weeks after surgery. For patients who develop a wound complication, we will track required therapies, including readmission to the hospital, reoperation, antibiotic therapy, wound opening with healing by secondary intention, including method of wound care and duration of wound healing. For patients requiring adjuvant therapy (chemotherapy and/or radiation), we will record duration from time of surgery to initiation of adjuvant therapy.

6.0 Patient Selection

Study entry is open to adult patients regardless of gender, race or ethnic background. While there will be every effort to seek out and include minority patients, the patient population is expected to mirror the obese patient population at the University Of Minnesota.

Inclusion Criteria

- 6.1 Known or suspected gynecologic or other abdominal malignancy (such as colorectal, liver, pancreatic, kidney and stomach) for which laparotomy is planned
- 6.2 Obese – defined as a Body Mass Index (BMI) ≥ 35 kg/m² as calculated in the Epic computer record
- 6.3 18 years of age or older
- 6.4 Able and willing to provide written consent

Exclusion Criteria

- 6.5 Known true tape allergy
- 6.6 Sensitivity to silver
- 6.7 History of intolerance to Negative Pressure Wound Therapy

[figure not shown]

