10.0 Statistical Considerations

10.1 Data Analysis

The patient population demographics will be descriptively summarized both combined and by treatment randomization. All analyses will be conducted under the intention-to-treat principle and all deviations and adverse events will be reported.

Our primary aim is to compare rate of wound complications (wound dehiscence or infection) identified within first month after surgery by treatment group (standard of care or NPWT). As this is a large randomized trial, the comparison will first be made using a Chi-squared test as we anticipate approximate balance in all measured and unmeasured confounders. These results will be supplemented using logistic regression, including demographics and clinical variables (including surgeon) as appropriate.

Our secondary aim is compare the time from surgery to starting adjuvant therapy among those with confirmed malignancies. This will be measured in days and will be available regardless if patients undergo treatment at our study facilities as their surgeon will manage their care and maintain contact up to 6 months regardless of follow-up location. The effect of NPWT on the length of the number of days until treatment will be assessed using Poisson regression, adjusting for over-dispersion if necessary. As stated above, we will supplement these results adjusting for demographic and clinical variables as appropriate.

For all analyses, p-values of less than 0.05 will be considered statistically significant and will be performed using SAS software version 9.3 (Cary, NC).

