10.2 Sample Size Calculations

As stated in the Section 4, we retrospective chart review of this patient population found 25% rate of wound complications. Group sizes of 97 each (194 total) achieves 80% power to detect a difference between the group proportions of -0.15; in other words, assuming the standard of care group has a complication rate of 25%, we could detect a complication rate in the NPWT group of 10% as being statistically significantly lower using a two-sized Z-test with a significance level of 0.05. This represents a clinically significant change in complication rates while remaining a feasible number to recruit within the study sites. Our proposed sample size is therefore 200 (100 in each group).

The secondary aim is not to formally test hypotheses but rather to describe this outcome and calculate preliminary estimates of differences. Among women undergoing this procedure at our study sites, approximately 70% will be

diagnosed with a malignancy, resulting in a sample size of 140 for this analysis. Among women in the standard of care group, we anticipate they will begin adjuvant therapy within 4-6 weeks after surgery. This sample size is more than sufficient (>90% power) to detect a difference of 1 day in time between surgery and beginning adjuvant therapy.

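### Patients are randomised before surgery on a planned laparotomy and all analysed by intention-to-treat, with no rule for those who end without a closed laparotomy incision; drawing the assignment at closure would remove most of the problem cheaply

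*Combined protocol and SAP*

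**What the plan says.** **Entry.** Criterion 6.1 requires a known or suspected gynecologic or other abdominal cancer ("such as colorectal, liver, pancreatic, kidney and stomach) for which laparotomy is planned"). The eligibility checklist in Appendix I repeats it. The condition is an intended operation, not a completed one.

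**Timing of assignment.** The synopsis states: "After screening and obtaining written consent, but prior to surgery 1:1 randomize to either". Section 7.0 ties randomisation to registration, and section 5.0 places it directly after consent.

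**Analysis population.** Section 10.1: "All analyses will be conducted under the intention-to-treat principle and all deviations and adverse events will be reported". The primary endpoint there is wound dehiscence or infection found in the first month after surgery.

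**Treatment.** Sections 5.0 and 8.2.2 place the device over the closed incision. Sections 5.0, 8.2.1 and 8.2.2 make skin closure by staples or suture a step in both arms.

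**Planning rate.** Section 4.0 takes it from a chart review of 51 obese patients who had a laparotomy, 13 of whom had a wound complication. Section 10.2 carries it forward: "assuming the standard of care group has a complication rate of 25"%. It then states "Group sizes of 97 each (194 total) achieves 80% power to detect a difference between the group proportions of -0.15" and rounds the total up to 200.

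**The concern.** The power calculation describes patients who have had a laparotomy. The analysis population is patients who were going to have one. Nothing in the available text connects the two.

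Three kinds of patient could fall in the gap: those whose operation is cancelled, those operated on without a laparotomy, and those whose skin is not closed at the end. Each stays in the denominator under intention-to-treat, yet none can show whether a device over a closed laparotomy incision helps. The plan has no replacement rule, outcome coding or named sample-size allowance for them.

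Two things are at stake. The absolute difference on which the trial is powered may be diluted, with some loss of power. And the analysts would have to decide how to code these patients after assignments are known, when that choice should be fixed in advance.

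**Working it through.** **Inputs.** From section 10.2: 25% in the control arm, 10% in the NPWT arm, a test at the 0.05 level (read as two-sided), 97 per arm calculated and 100 per arm planned. The affected share q is not in the documents; 3% to 10% is assumed.

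**The plan's own figure.** With unpooled variance:

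n = (1.960 + 0.842)² × (0.25×0.75 + 0.10×0.90) / 0.15² = 96.8, so 97 per arm.

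This matches the plan, so its arithmetic is not at fault.

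**Formula for the rest.** The pooled Z-test corresponds to the uncorrected Chi-squared test, so I use it below:

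power = Φ{ [ |p1 − p2|√n − 1.960√(2p̄(1 − p̄)) ] / √(p1(1 − p1) + p2(1 − p2)) }

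Baseline, n = 100: p̄ = 0.175, and (1.500 − 1.053)/0.527 = 0.848, giving **80.2%**. The unpooled version gives 81.3%.

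**Scenario A: share q of both arms has no laparotomy incision and is counted as event-free.** Both rates are multiplied by (1 − q).

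| q | Control | NPWT | Difference (points) | Power, 100 per arm | n per arm for 80% |
|---|---|---|---|---|---|
| 0 | 25% | 10% | 15.0 | 80.2% | 100 |
| 3% | 24.25% | 9.7% | 14.55 | 78.7% | 104 |
| 5% | 23.75% | 9.5% | 14.25 | 77.7% | 106 |
| 10% | 22.5% | 9.0% | 13.5 | 74.9% | 114 |

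The risk ratio stays at 0.40 throughout. If such patients instead had an assumed 3% event rate from a minimally invasive wound, power at q = 10% would be 74.3%.

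**Scenario B: share q of the NPWT arm cannot have the device placed and stays at 25% risk.** The NPWT rate becomes 10% + 15% × q and the control arm is unchanged.

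| q | NPWT | Difference (points) | Power, 100 per arm | n per arm for 80% |
|---|---|---|---|---|
| 3% | 10.45% | 14.55 | 77.3% | 107 |
| 5% | 10.75% | 14.25 | 75.2% | 113 |
| 10% | 11.5% | 13.5 | 69.8% | 128 |

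Here the risk ratio is diluted too: 11.5/25 = 0.46 at q = 10%.

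**Slack.** 200 − 194 = 6 patients, about 3%. On the unpooled formula, scenario A at 3% gives 79.8%, so the margin is roughly used up there.

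**Excluding affected patients after randomisation.** At q = 10% this leaves 90 per arm. The difference returns to 15 points, but power is 75.9%, against 74.9% with everyone kept under scenario A.

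**The case against.** Several objections carry weight.

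- **Intention-to-treat over patients randomised before surgery is legitimate.** Dilution under it is conservative for a superiority claim. This stands: the point concerns when the assignment is drawn, not the principle.
- **The documents do not show that such patients are common.** A reader might take section 1.0 ("Some patients are able to circumvent this problem with a minimally invasive approach to their surgery") as evidence that planned laparotomies turn into minimally invasive ones. It is not. The sentence goes on to say that obesity makes conversion to open surgery more likely, which is the opposite direction, and it gives no rate. Skin left open is not mentioned anywhere; under sections 5.0 and 8.2 it would be a departure from the described closure, and deviations are to be reported.
- **A reader might infer that the plan codes these patients as complication-free.** It does not say so. The endpoint is not limited to laparotomy wounds, so a minimally invasive wound could have an event. A cancelled operation has no period after surgery, so its outcome is undefined. Event-free coding is an assumption of scenario A.
- **Scenario B is narrower than the gap.** It models failure to place the device in one arm, whereas skin left open could occur in both.
- **Silence cannot be fully confirmed.** A figure after the eligibility criteria is not shown, and section 8.1 has no visible content in the text available.

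None of this supplies a rule for these patients or makes the randomised population match the one behind the planning rate.

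**Conclusion.** The mismatch is real and its likely effect is modest. Entry and assignment rest on an intended laparotomy, while the treatment and the 25% planning rate presuppose a completed one; no outcome coding is stated for patients in between.

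At an assumed 3% to 10%, power falls from 80.2% to about 79% to 75% in scenario A, with the difference at 14.6 to 13.5 points and the risk ratio unchanged. In scenario B it falls to about 77% to 70%. These ranges rest on an assumed share and, for A, on an assumed coding.

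The documents do not support the stronger reading that the comparison is seriously compromised. Nor do they support replacing intention-to-treat with a restricted primary analysis set. That would recover about one point of power at 10%, and it would condition on something that happens after randomisation in a trial where no blinding of the surgeon is described. This is an inexpensive improvement to the design, not an error in the analysis principle.

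**What to change.** In section 7.0, and correspondingly in the synopsis and section 5.0, keep consent and registration before surgery. Draw the 1:1 assignment in the operating room, once the laparotomy has been done and the surgeon has declared that the skin will be closed. Complete the assignment line on the Appendix I checklist at that point. Keep intention-to-treat over all randomised patients as the primary analysis. The 200 are then patients with a laparotomy whose closure was declared before the arm was known, which fits the population behind the power calculation.

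The cost is a protocol amendment, an assignment step in the operating room, and somewhat more patients consented than randomised: 200/(1 − q), or about 207 at 3% and 223 at 10%. No study procedure is added.

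If randomisation before surgery must stay, keep intention-to-treat as primary. State in section 10.1 how the outcome is coded for patients without a closed laparotomy incision, report their number by arm, and give a supportive analysis that excludes them.

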7.0 Patient Registration and Randomization

Patients will be registered into OnCore after written consent is provided and eligibility is confirmed (appendix I), but prior to the performance of any research related procedures.

Randomization will occur at the time of registration. To prevent bias and minimize the possibility of confounding, consenting patients will be randomly assigned 1:1 to either NPWT or standard of care.

8.0 Study Procedures

8.1 Study Plan

8.2 Assigned Care (Standard Closure and Wound Care vs. Standard Closure with Negative Pressure Wound Therapy)

8.2.1 Standard Closure and Wound Care

The standard surgical closure consists of closure of the fascia with a looped PDS suture in a running fashion either in with the use of a mass closure technique or a Smead Jones closure at the discretion of the operating surgeon, closure of the subcutaneous space if >2 cm deep, followed by staple or suture closure of the skin.

Post-operative wound care will be standard of care per institutional guidelines.

8.2.2 Standard Closure and Negative Pressure Wound Therapy

The same standard surgical closure as used by the standard of care group will be used for patients randomized to prophylactic placement of the Prevena™ Incision Management System. As in the previous section it consists of closure of the fascia with a looped PDS suture in a running fashion either in with the use of a mass closure technique or a Smead Jones closure at the discretion of the operating surgeon, closure of the subcutaneous space if >2 cm deep, followed by staple or suture closure of the skin.

The Prevena™ Incision Management System will be placed over the closed incision. It will be removed on post-operative day 2 or 3 as clinically indicated and prior to the patient's discharge from the hospital.

8.3 Risks of Study Participation

8.3.1 Standard of Care

Risks to the patients randomized to standard of care will be no different than undergoing the same surgical procedure without participating in this study.

